3.3 Study Design

This is a single-center and randomized design where each subject receives two different treatments out of 4 treatments, one on the left side of the body and one on the right side. This means there are 6 possible combinations of treatments (assuming A, B and C are either Investigational Product #1, Investigational Product #2 or Active Control, D is the Negative Control): A & B, A & C, A & D, B & C, B & D, and C & D.

A minimum of 72 evaluable subjects will be required to achieve a total of at least 144 test sites for groin and abdominal regions. To achieve 36 evaluable test sites from Investigational Product 1, Investigational Product 2, Active Control and Negative Control arms for groin and abdominal regions, of the minimum 72 evaluable subjects:

- 12 subjects will receive treatments from both A and B.
- 12 subjects will receive treatments from both A and C.
- 12 subjects will receive treatments from both A and D.
- 12 subjects will receive treatments from both B and C.
- 12 subjects will receive treatments from both B and D.
- 12 subjects will receive treatments from both C and D.

The two investigational products and the active control will be randomly assigned codes of A, B or C. However, due to visual differences between each of the test materials, the products cannot be blinded to all study staff. In order to guard against any bias of the study outcome, technicians who participate in product application or sample collection from subjects during treatment day procedures will not participate in the processing of samples. The technicians processing samples and/or counting the resultant plates will be blinded to the study randomization during the data gathering processes. Plate counts will be reviewed and recorded by separate BSLI staff prior to being entered into a data spreadsheet where product information (unblinding) would occur.

Subjects will be sampled for treatment day baseline microbial populations on randomly assigned sites of the abdominal and inguinal areas on both sides. Subjects will have samples collected at baseline, 30 seconds (± 5 seconds), 10 minutes (± 30 seconds) and at 6 hours (± 30 minutes) post-treatment application on both abdomen and inguinal sites. All sampling times will be calculated from the completion of the dry time of each product following application.

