7.3 Analysis Methods

For each body site, when per-protocol data are different from mITT data for average treatment effect (ATE), responder rate, log reduction or product expression volumes, per-protocol analysis and mITT analysis will be performed separately using the same statistical methods. The following analysis methods will be applied to both per-protocol analysis and mITT analysis, both abdomen and groin.

An alpha level of 5% (two-sided) is used for all analyses.

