7.3.3.2 Log Reduction

\log_{10} reductions will be compared between test materials by an Analysis of Variance (ANOVA) for each body site based on mITT data and/or per-protocol data. In the ANOVA model, the response is the \log_{10} reduction and the predictors are treatment and time point as well as the interaction between treatment and time point. The average difference in log reduction between treatments per time point will be estimated. However, all conclusions for the difference in the average treatment effect between treatments will be based on the primary analysis only.

An example for results of comparisons above can be found in Tables 10.

Table 10: Example: results for product comparisons within time interval (10 minutes) for Groin

Comparison	N Pairs	Difference	Conf Int	Conclusion
IP1 Baseline-A 10 min vs. AC Baseline-AC 10 min	36	0.13	-0.44, 0.70	no sign. diff.
IP2 Baseline-A 10 min vs. AC Baseline-AC 10 min	36	0.11	-0.65, 0.87	no sign. diff.
IP1 Baseline-A 10 min vs. VC Baseline-VC 10 min	36	0.33	-0.44, 1.09	no sign. diff.
IP2 Baseline-A 10 min vs. VC Baseline-AC 10 min	36	0.33	-0.44, 1.09	no sign. diff.

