7.3.3.3 Product Expression Volumes/Weight

An analysis of variance (ANOVA) of the applied volumes/weight will be performed separately for each body site based on mITT data and/or per-protocol data. In the model, there will be a random subject effect, a fixed body side (left or right) effect, a fixed treatment effect and the interaction between fixed effects. ANOVA table will be checked to see whether the treatment has a significant effect on product expression volumes as well as the interaction. If a significant difference is found, subgroup comparisons with Tukey’s method will be made to determine which pair of comparisons shows significant difference.

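### The exploratory log-reduction ANOVA has no subject or site effect, so its per-time-point intervals would be modestly too wide

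*SAP*

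**What the plan says.** SAP 7.3.3.2 fits one ANOVA per body site to the log10 reductions; its "predictors are treatment and time point as well as the interaction between treatment and time point". Protocol 7.3 and 15.3 name the same terms. None of the three sections names a subject term, a site term, a repeated-measures covariance or a variance that differs by arm or time.

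The output is a set of contrasts at each time: "The average difference in log reduction between treatments per time point will be estimated". The layout is only illustrated: "An example for results of comparisons above can be found in Tables 10". SAP 7.3 sets the level: "An alpha level of 5% (two-sided) is used for all analyses". The role is limited: "all conclusions for the difference in the average treatment effect between treatments will be based on the primary analysis only".

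On the design, SAP 3.3 says "each subject receives two different treatments out of 4 treatments, one on the left side of the body and one on the right side", and "A minimum of 72 evaluable subjects will be required to achieve a total of at least 144 test sites", with 12 subjects for each of the six product pairs. Protocol 13.3 has each site sampled once at baseline and once at each of three later times. SAP 7.1.2 forms every reduction by subtracting the later count from the baseline.

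The next section of the SAP, 7.3.3.3, handles product weight under this same design differently: "there will be a random subject effect, a fixed body side (left or right) effect".

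**The concern.** A plain ANOVA treats every reduction as independent, with one residual variance. Here two reductions at the same time can come from one subject under two products, and the reductions at one site at different times share both the skin site and its single baseline count. The SAP allows for the subject in the product-weight analysis but not in this microbiological one.

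At stake are the stated widths of the intervals in the exploratory comparison and the precision that the paired layout offers. The declared purpose of the study is to inform the design of later ones, so honest interval widths have some value even for an exploratory analysis.

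**Working it through.** **The plan's own figure.** Table 10 (groin, 10 minutes) shows intervals with half-widths 0.57, 0.76, 0.765 and 0.765, for example (0.70 + 0.44)/2 = 0.57. A balanced ANOVA with one residual variance must give the same half-width in every row. Taking the 12 example SDs in Table 9, the pooled SD is s = √(13.8141/12) = 1.073. With 144 × 3 − 12 = 420 degrees of freedom, the half-width is 1.966 × 1.073 × √(2/36) = 0.497. Using two time points, 10 minutes alone, or separate two-sample comparisons gives 0.468 to 0.534. Table 10 is not reproduced, and its rows read as placeholders.

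**Inputs.** 36 sites per product and body site; 12 subjects shared by any two products (SAP 3.3). The side-to-side correlation ρ is not in the documents and is assumed. The formulas use the planned balance; sites lost on Treatment Day baseline would break some pairs.

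**1. Two products in one subject.** The covariance of two product means at one time is 12ρs²/36². So

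Var(difference) = 2s²/36 − 2 × 12ρs²/36² = (2s²/36)(1 − ρ/3).

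The ANOVA uses 2s²/36. Its nominal SE is too large by the factor 1/√(1 − ρ/3):
- ρ = 0.2: 1.035
- ρ = 0.4: 1.074
- ρ = 0.6: 1.118
- ρ = 0.8: 1.168

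**2. Repeated times at one site.** Correlation over time, including that from the shared baseline, does not enter the variance of a mean at a single time. It only overstates the degrees of freedom: t is 1.966 at 420 and 1.977 at 140, a difference of 0.6%.

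**3. Precision available from the pairs.** The efficiency of the within-subject comparison is 12 × 4/(36 × 2) = 2/3, equivalent to 24 of the 36 sites, leaving 12 for between-subject information. With ρ treated as known,

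Var = 2s²/[24/(1 − ρ) + 12/(1 + ρ)].

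- ρ = 0.2: 24/0.8 + 12/1.2 = 40; SE ratio to the ANOVA √(36/40) = 0.95.
- ρ = 0.4: 24/0.6 + 12/1.4 = 48.57; SE ratio √(36/48.57) = 0.86.

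On the Table 9 example SDs, the half-width of 0.497 would fall to about 0.47 and 0.43. Estimating ρ would cost a little of this gain.

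**4. Simulated coverage, equal SDs** (72 subjects, three times, 4,000 trials per setting). Nominal 95% intervals at each time covered 94.5% to 95.4% with no correlation, about 95% with correlation over time only, and 95.3% to 97.1% with side-to-side correlation 0.2 to 0.5.

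**5. Simulated coverage, unequal SDs (assumed).** With relative SDs of 0.82, 0.82 and 1.26 over the three times, coverage was 98.7%, 98.9% and 89.5%. With 1, 0.83 and 1.15 it was 95.9%, 99.0% and 93.6%. With SDs equal over time but a saline SD of 0.5 against 1.1 elsewhere, a separate simulation at correlation 0.2 to 0.4 gave 93% to 95% for investigational product against active control. None of these SDs comes from the documents.

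**6. Which times are compared.** SAP 7.3.3.2 gives no number of time points. Protocol 15.3 lists 30 seconds, 10 minutes and 6 hours for the descriptive statistics, but its sentence on comparing products refers to only two post-treatment times. Three times would mean 144 × 3 = 432 values per body site; two would mean 144 × 2 = 288.

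**The case against.** The best defence is that little depends on this analysis. It is exploratory, the study is not powered for efficacy, and both documents reserve treatment conclusions for the primary model, which adjusts for baseline. For the contrasts reported, the omission errs on the cautious side. All of this stands, and it is why the point ranks low. It does not explain why product weight gets a subject effect and log reduction does not.

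Several stronger readings are tempting, and the documents do not support them:
- **That the Table 10 intervals and its entries of no significant difference are wrong.** The table is an example without trial data, and its widths could not come from the balanced common-variance model described. Nor does its column of 36 pairs point to a paired analysis: the design gives 12 within-subject pairs per comparison.
- **That ignoring the correlation inflates false positives.** That holds for the overall treatment F test averaged over times (12% to 27% rejection at a nominal 5% in the equal-SD simulations with correlation), but the SAP reports differences at each time.
- **That the intervals are wrong in both directions.** Under-coverage appears only when unequal SDs are assumed. The Table 9 SDs lie between 0.89 and 1.18 in every cell, including saline, but they are examples and settle nothing either way.
- **That this is the only planned 6-hour comparison between products.** Whether 6 hours is included is unclear, and SAP Tables 3 and 4 carry columns for a 6-hour average treatment effect.

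**Conclusion.** The point holds as a low-importance improvement. The model in SAP 7.3.3.2 omits the subject and site structure that the design creates and that SAP 7.3.3.3 partly recognises. If the two sides of a subject are positively correlated, the per-time-point intervals are modestly too wide: nominal SE 3.5% too large at a correlation of 0.2 and 7% at 0.4. Using the within-subject pairs would bring the SE to about 0.95 and 0.86 of the ANOVA's. These sizes rest on the assumed correlations, the planned 12 subjects per pair and a common variance. Intervals that are too narrow remain a possibility if SDs differ by arm or time, but the documents give no trial SDs with which to judge it. Nothing here touches the primary conclusions.

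**What to change.** In SAP 7.3.3.2, keep treatment, time point and their interaction, and add a random subject effect and a random side-within-subject effect for each body site, with residual variance allowed to differ by time point. A simpler alternative is to fit each time point separately with a random subject effect, which gives each time its own variance without further modelling. Report the same contrasts at each time. A baseline covariate, or variances that also differ by arm, would go further than this point requires.

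State in SAP 7.3.3.2 which time points are compared, and reconcile Protocol 15.3 so that the comparison and the descriptive statistics agree on whether 6 hours is included.

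The cost is a few sentences of wording and a standard mixed-model call in R, the software the SAP already names. No new data are needed.

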7.3.3.3 Product Expression Volumes/Weight

An analysis of variance (ANOVA) of the applied volumes/weight will be performed separately for each body site based on mITT data and/or per-protocol data. In the model, there will be a random subject effect, a fixed body side (left or right) effect, a fixed treatment effect and the interaction between fixed effects. ANOVA table will be checked to see whether the treatment has a significant effect on product expression volumes as well as the interaction. If a significant difference is found, subgroup comparisons with Tukey’s method will be made to determine which pair of comparisons shows significant difference.

7.3.4 Safety Analysis

The ITT data set (all randomized subjects) will be considered evaluable for safety. Skin irritation scores will be reported for any subject who is scored with a 1 or more at any observation [baseline, post-application/prior to 30 seconds, 10 minutes, and 6 hours sampling procedures], in any category for any site.

Adverse Events (including post treatment skin irritation scores of 3), will also be summarized. Summary tables will present incidence rates of adverse events by treatment group for all subjects who enter the treatment period. Listings of Adverse Events will be provided.

The statistical significance of differences in skin irritation between the Investigational Products, Active Control and Negative Control will be evaluated using Fisher’s exact test on skin irritation data summarized as follows: any reaction above zero (no reaction) on the skin irritation rating scale for any category (erythema, edema, rash, and dryness) will be considered a positive signal for that substance. If Fisher’s exact test shows there is an overall significant treatment effect, Fisher’s exact test or two-proportion test with Score method with multiplicity adjustment on the alpha level may be used for multiple sub-group comparisons to find out which comparisons show the difference. Odds ratio (odds of having positive signals for one treatment / odds of having positive signals for the other treatment) using Fisher’s exact test or the difference in percentage of positive signals between treatments using Two-proportion test may be calculated along with the confidence interval for each category at the certain time interval. The analysis for skin irritation scores will be for informational purposes only.

Examples for Fisher’s exact test and two-proportion test with Score method are shown below.

```
> # overall treatment effect
> irr_tab <- matrix(c(2, 1, 3, 1, 34, 35, 33, 35),
+   nrow = 4,
+   dimnames =
+   list(c("A", "B", "C", "D"),
+   c("Positive (Score > 0)", "Non-positive (Score = 0)")))
> irr_tab
```

	Positive (Score > 0)	Non-positive (Score = 0)
A	2	34
B	1	35
C	3	33
D	1	35

```
> irr <- fisher.test(irr_tab, alternative = "two.sided",
+   conf.level = 0.95)
> print(irr)
```

Fisher's Exact Test for Count Data

```
data: irr_tab
p-value = 0.8361
alternative hypothesis: two.sided
```

```
> # subgroup comparisons
> library(PropCIs)
> print(diffscoreci(2, 34, 1, 35, conf.level = 0.972))
```

```
data:
97.2 percent confidence interval:
-0.1176006 0.1904725
```

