### **13.3 Randomization**

The randomization scheme for the study will be provided by the Study Sponsor. The test materials will be coded as A, B, C, and D and assigned randomly to the subjects per a computer-generated randomization schedule in blocks of 24 subjects. Subjects will be randomized to test all of the Treatment Groups.

Each subject will receive two different treatments, one on the right side of the body and one on the left. The 6 possible combinations for product application is as follows:

- Treatment A / Treatment B
- Treatment A / Treatment C
- Treatment A / Treatment D
- Treatment B / Treatment C
- Treatment B / Treatment D
- Treatment C / Treatment D

A minimum of 72 evaluable subjects will be required to achieve 36 evaluable test sites for each test material: Investigational Product #1, Investigational Product #2, Active Control, and Negative Control arms for inguinal and abdominal regions (at least 144 total test sites for inguinal and abdominal regions).

Subjects will be randomized to treatment using the following block design:

- The study product assignments will be balanced such that the number of readings per anatomical site matches the calculated requirements.
- The application will be randomized so that each treatment is used on an equal number of left and right sides of the body.
- Each inguinal and abdominal sample site is divided into four areas, and all four of the areas are sampled: one at baseline, one at 30 seconds, one at 10 minutes, and one at 6 hours. Therefore, for any inguen or abdomen site there are 24 possible sampling orders.

The number of subjects required for a completely balanced block design for all factors at once (study products, left/right, and sampling order) is a multiple of 288 (6\*2\*24). The number of intended subjects makes it infeasible to provide a completely balanced block design, so the following priority order will be used for design:

1. Treatment combinations will be applied in balanced blocks
2. Left/right balance will be preserved – each treatment will be applied an equal number of times to each side of the body.
3. Sampling orders will be assigned in blocks of 24 as much as possible. If the final number of subjects is not a multiple of 24 the remaining subjects will be assigned random non-duplicate sample orders from the 24 possible sample orders.

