### 15.4 Safety Analyses

The ITT data set (all randomized subjects) will be considered evaluable for safety. Skin irritation scores will be reported for any subject who is scored with a 1 or more at any observation [baseline (screening day and treatment day), post-application/prior to 30-second, 10-minute, and 6-hours sampling procedures], in any category for any site.

Adverse Events (including post treatment skin irritation scores of 3), will also be summarized. Summary tables will present incidence rates of adverse events by treatment group for all subjects who enter the treatment period. Listings of Adverse Events will be provided.

The statistical significance of differences in skin irritation between the Investigational Products and Active Control will be evaluated using Fisher's exact test on skin irritation data summarized as follows: any reaction above zero (no reaction) on the skin irritation rating scale for any category (erythema, edema, rash, and dryness) will be considered a positive signal for that substance. If Fisher's exact test shows statistically significant skin irritation between the three study products, a secondary analysis will be conducted to determine how the reactions differ.

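### The skin-irritation tests ignore that each subject carries two of the compared products; with one record per side and positive left/right correlation they are conservative and give up power, in an analysis the SAP treats as informational

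*SAP*

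**What the plan says.** Protocol 13.3 sets the design: "Each subject will receive two different treatments, one on the right side of the body and one on the left". SAP 3.3 gives the minimum size, "A minimum of 72 evaluable subjects will be required to achieve a total of at least 144 test sites for groin and abdominal regions", and spreads the subjects evenly over the six product pairs, for example "12 subjects will receive treatments from both A and B".

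For irritation, SAP 7.3.4 says "The statistical significance of differences in skin irritation between the Investigational Products, Active Control and Negative Control will be evaluated using" Fisher's exact test, where any score above zero in any category counts as positive. The R example builds the table with "irr_tab <- matrix(c(2, 1, 3, 1, 34, 35, 33, 35", which is four products by two outcomes with no subject identifier. If the overall test is significant, follow-up comparisons may use Fisher's test or a two-proportion score method, both unpaired. Protocol 15.4 plans the same kind of test but names fewer products: "The statistical significance of differences in skin irritation between the Investigational Products and Active Control will be evaluated using" Fisher's exact test.

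The level comes from SAP 7.3: "An alpha level of 5% (two-sided) is used for all analyses". For product expression, SAP 7.3.3.3 does allow for the shared subject: "In the model, there will be a random subject effect". Nothing equivalent is specified for irritation.

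**The concern.** The hypothesis of interest is that the products do not differ in irritation. Fisher's test on this table takes its reference distribution from scattering the positives at random over 144 independent units. That describes no product effect and also no association between a subject's two sides. If a subject who reacts on one side tends to react on the other, part of the between-subject variation cancels when products are compared. The test does not use this cancellation. It rejects too rarely under the null and forgoes power that the paired allocation makes available.

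The documents give no correlation but make a positive one plausible. Protocol 14.2 expects scores of 1 or 2 after sampling and application. Protocol 14.4 anticipates abrasion from cup sampling and folliculitis from clipping. These procedures affect both sides of the same person.

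Protocol 7.5 names irritation scores as one of two principal safety measures, and the study is meant to inform later trials. A conservative overall test leans towards reporting no difference, and the multiple comparisons depend on that overall test.

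**Working it through.** **Inputs.** There are 72 subjects, 12 per product pair and 36 sides per product in each region (SAP 3.3, Table 1). Alpha is 0.05 two-sided (SAP 7.3). The left/right correlation rho of the binary outcome is not in the documents, so a range is assumed. The safety set is all randomized subjects, so 144 sides per region is a minimum.

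**1. The plan's own figure.** Full enumeration of the table with positives 2, 1, 3, 1 and non-positives 34, 35, 33, 35 gives p = 0.8361, as the SAP prints. The calculation uses only the four counts, so p is the same however the 7 positives (7/144 = 4.9%) fall within subjects.

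**2. Variance of a product difference, one record per side.** Let s² be the variance of one record.
- Each product mean has variance s²/36.
- Two product means share 12 subjects, so their covariance is 12·rho·s²/36² = rho·s²/108.
- Variance of the difference = 2(s²/36) − 2(rho·s²/108) = (s²/18)(1 − rho/3).

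The unpaired test assumes s²/18, which is too large when rho > 0.

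**3. Size.** The large-sample size of the four-product test is P(chi-square, 3 df > 7.81/(1 − rho/3)). For one pair it is 2[1 − Φ(1.96/√(1 − rho/3))]. Simulation of the 72-subject design used 6,000 null runs at a 20% rate. It compared Fisher with a re-randomization test that keeps each subject's two results together.

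| rho | 1 − rho/3 | Four-product size | Pairwise size | Fisher, simulated | Pair-preserving, simulated |
|---|---|---|---|---|---|
| 0 | 1.000 | 5.0% | 5.0% | 4.4% | 4.4% |
| 0.3 | 0.900 | 3.4% | 3.9% | 3.3% | 4.4% |
| 0.5 | 0.833 | 2.5% | 3.2% | 2.4% | 4.6% |
| 0.7 | 0.767 | 1.7% | 2.5% | 1.8% | 4.4% |

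A separate simulation at correlation 0.5-0.6 gave about 1% for Fisher and 4% for the pair-preserving test. At a 5% rate, near the SAP example, discreteness lowers both further: 2.6% and 3.5% at rho 0, then 0.6% and 2.4% at rho 0.5.

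**4. Power, same count statistic for both tests (4,000 runs; Fisher → pair-preserving).**

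| Rates in the four products | rho 0 | rho 0.3 | rho 0.5 |
|---|---|---|---|
| 5/5/5/20% | 52.1 → 55.9% | 51.5 → 59.9% | 51.5 → 63.2% |
| 10/10/10/30% | 60.1 → 62.8% | 61.2 → 68.3% | 58.5 → 70.0% |
| 20/20/10/5% | 46.0 → 43.4% | 45.9 → 48.4% | 42.6 → 49.4% |
| 40/40/40/20% | 42.5 → 40.1% | 41.2 → 45.2% | 39.7 → 49.2% |
| 20/20/20/50% | 80.4 → 81.5% | 81.8 → 86.2% | 82.4 → 89.5% |

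The gain is about 2 to 8 points at rho 0.3 and 7 to 12 at rho 0.5. At rho 0 it runs from −2.6 to +3.8 points. Fisher's own power stays roughly level as rho rises. The loss is measured against what the design could deliver.

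**5. Power with a correlation-weighted score statistic.** At correlation about 0.5-0.6 (800 runs):
- both investigational products 50%, controls 30%: 49 → 77%
- one investigational product 50%, others 30%: 36 → 62%
- both investigational products 25%, controls 10%: 48 → 70%

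These are gains of 22 to 28 points. A 500-run repeat at correlations of about 0.3-0.6 gave 20 to 29. The standard error of each power figure is about 2 points (√(0.5·0.5/500) = 0.022). At 0.2-0.3 the gain was 8 to 13 points.

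**6. If abdomen and groin were pooled as separate records.** Each product then has 72 records, two per side. Assume a common correlation rho between all records of a subject.
- Variance of a product mean = (s²/72)(1 + rho).
- Covariance of two product means = 12·4·rho·s²/72² = rho·s²/108.
- Variance of the difference = (s²/36)(1 + rho/3).

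The assumed value is s²/36, now too small, so the test over-rejects. A chi-square version simulated at a 20% rate gave 5.8-8.7% against a nominal 5%.

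**The case against.** The strongest reply is that little hangs on this p-value. SAP 7.3.4 describes the irritation analysis as informational, the study is an unpowered Phase II, and no success criterion uses the test. This stands, and it limits the weight of the point.

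A reader might infer that a real irritation difference would be hidden and the follow-up never opened. The documents do not support that. Every score of 1 or more is reported, and scores of 3 are adverse events summarized by treatment. The odds ratios or risk differences with intervals appear in a sentence of SAP 7.3.4 that sets no significance condition. Only the multiple comparisons are conditional on the overall test.

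It is also fair to say that the correlation is undocumented. Protocol 11.4 and 14.2 exclude or defer subjects with a score of 1 before sampling or application, which removes some already reactive people. The effect is therefore conditional. Its direction also depends on the record unit: SAP 7.3.4 does not say whether the regions are tabled separately, although its example of 36 per product points that way.

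The larger power figures need care as well. With one product at 50% and the others at 30%, power was 38% for Fisher, 49% for the pair-preserving test on the same counts, and 66% with the weighted statistic. Of those 28 points, 11 come from respecting the pairs and 17 from the more efficient statistic. Nearer the example rate, at correlation about 0.3, one product at 15% against 5% gave 25 → 38%, and two products at 10% against 5% gave about 10 → 15%. Both tests are weak there.

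**Conclusion.** The unpaired tests do not match the design. With one record per side and a positive left/right correlation, they are conservative. At a 20% irritation rate, size is about 3-3.5% at correlation 0.3 and about 1-2.5% at 0.5. The power given up is roughly 2-13 points at correlation 0.2-0.3 and roughly 7-28 points at 0.3-0.6, depending on rates and statistic, with no material loss at zero correlation.

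These sizes rest on assumed correlations and rates, 12 subjects per pair, and one record per side within a region. It would go too far to say that the test certainly under-rejects or will miss a real difference: the documents fix neither the correlation nor, beyond the example, the record unit. No efficacy conclusion is affected. The change is still worth making, because irritation is a principal safety measure and the same SAP already models the subject for product expression.

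**What to change.** In SAP 7.3.4, with matching wording in Protocol 15.4:

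- State that the test is run separately for abdomen and groin, with one record per side. Say which time point, or combination of time points, that record represents.
- Replace the overall Fisher test with a re-randomization test that keeps each subject's two results together and permutes product pairs and sides across subjects. A score statistic weighted for the within-subject correlation is preferable. Keep Fisher as a descriptive check.
- Apply the same pair-preserving approach to IP − AC and IP − NC, re-labelling only the two products compared.
- Report risk differences with intervals that allow for the shared subjects only where event counts permit. Do not rely on cluster-robust GEE intervals with sparse or zero counts. The SAP example has 1 to 3 events per product.

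An analysis of discordant pairs alone is not a good substitute. Its contrast variance is (s²/12)(1 − rho), against (s²/18)(1 − rho/3) for the unpaired difference. It is better only when rho exceeds 12/28, about 0.43.

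The cost is SAP and protocol wording and a little more programming than a single Fisher call. No new data are needed.

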## 7.5 Safety Analysis

The full Intent-to-Treat data set (all randomized subjects) will be used for the safety analysis. The principal measures of safety will be skin irritation scores and the incidence of adverse events reported during the study.

Differences between both Investigational Products, Active Control, and Negative Control will be evaluated on skin irritation data.

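### The SAP's example code for pairwise skin-irritation comparisons enters the non-positive counts (34, 35) as sample sizes; its own table has 36 sites per arm

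*SAP*

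**What the plan says.** SAP 7.3.4 (Safety Analysis) classes any irritation score above zero, in any category, as a positive signal. It compares the four treatments with an overall Fisher's exact test. If that test is significant, the section allows either further Fisher tests or a score method: "two-proportion test with Score method with multiplicity adjustment on the alpha level may be used for multiple sub-group comparisons". For the score method it names the quantity to be estimated: "the difference in percentage of positive signals between treatments using Two-proportion test may be calculated".

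Worked R code follows. The example table is built by "irr_tab <- matrix(c(2, 1, 3, 1, 34, 35, 33, 35", with one column for positive sites and one for non-positive sites. The overall Fisher test on it prints p = 0.8361. The pairwise example, A against B, is then "print(diffscoreci(2, 34, 1, 35, conf.level = 0.972", and its printed limits are minus "0.1176006 0.1904725".

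The same section limits the weight of all this: "The analysis for skin irritation scores will be for informational purposes only".

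**The concern.** A score interval for a difference of two proportions needs, for each arm, the number of positives and the number of sites. The example supplies the positives and the non-positives. It therefore works with x/(n - x), which is an odds, where the text asks for x/n, a percentage.

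This is the SAP's only worked code for the pairwise score method, so it is a natural template for the analysis program. An odds is always larger than the matching proportion, and the gap widens as reactions become more common, so reuse on trial data would inflate differences between arms. Protocol 14.2 says that scores of 1 or 2 are to be expected after sampling and application, and any score above zero counts as positive. Rates well above those in the example are therefore possible, although neither document gives an expected rate. The practical risk is an apparent irritation difference, for instance between an Investigational Product and the Active Control, that the data do not support.

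**Working it through.** **Inputs (SAP 7.3.4).**

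| Arm | Positive | Non-positive | Total |
|---|---|---|---|
| A | 2 | 34 | 36 |
| B | 1 | 35 | 36 |
| C | 3 | 33 | 36 |
| D | 1 | 35 | 36 |

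The totals agree with the 36 evaluable sites per arm in SAP sections 3.3 and 4. The confidence level is 97.2%.

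**Method.** The interval is the Miettinen-Nurminen score interval. For a candidate difference d,

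z²(d) = (p1 - p2 - d)² / { [q1(1 - q1)/n1 + q2(1 - q2)/n2] × N/(N - 1) },

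where p1 = x1/n1, p2 = x2/n2, N = n1 + n2, and q1, q2 are the maximum-likelihood proportions constrained to q1 - q2 = d. The limits are the values of d at which z²(d) equals the 0.972 quantile of chi-square on 1 df, 4.828.

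**Step 1: reproduce the printed interval, A v B.**

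| Inputs (x1, n1, x2, n2) | Point difference | 97.2% interval |
|---|---|---|
| 2, 34, 1, 35 (as coded) | 2/34 - 1/35 = 0.0303 | -0.1176006 to 0.1904725 |
| 2, 36, 1, 36 (table totals) | 2/36 - 1/36 = 0.0278 | -0.1160526 to 0.1806500 |

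The first row matches the SAP's output to all seven decimals. The example was run with 34 and 35 as denominators. Its upper limit is too high by 0.1905 - 0.1807 = 0.0098.

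**Step 2: rule out 34 and 35 as true arm totals.** The exact Fisher p-value for 2, 1, 3 and 1 positives is 0.8361 with 36 sites per arm, as printed. With totals of 34, 35, 33 and 35 it would be 0.5415. The SAP's own overall test therefore confirms 36 per arm, and its two adjacent examples use incompatible denominators.

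**Step 3: the example's widest contrast, C v B (3 v 1).** As coded the interval is -0.0902 to 0.2361; with 36 per arm it is -0.0920 to 0.2179. Neither excludes zero.

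**Step 4: where reuse would change a conclusion.** Take 36 sites per arm at 97.2% and list every unequal pair with at most 17 positives in the higher arm (above 18 the coded proportion exceeds 1). There are 17 × 18/2 = 153 pairs.

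- 28 exclude zero only as coded; none does so only with the correct totals.
- None of the pairs with 5 or fewer positives in the higher arm changes.
- The smallest that changes is 6 v 1: 0.0008 to 0.3746 as coded, -0.0203 to 0.3190 correct. The other 27 need at least 8 of 36 in the higher arm.

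**Step 5: error rate for one pair.** Exact binomial sums, 36 independent sites per arm, equal true rates (assumed), without the overall Fisher gate. The nominal rate is 100% - 97.2% = 2.8%.

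| True rate | As coded | Correct |
|---|---|---|
| 3% | 0.33% | 0.29% |
| 5% | 1.5% | 1.1% |
| 10% | 5.2% | 2.7% |
| 20% | 10.5% | 2.7% |

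**Step 6: error rate with the overall Fisher test as gate.** Chance of at least one declared difference among three equally irritating products, in 20,000 simulated trials per row. The overall four-arm Fisher p must be at most 0.05; the three product pairs are then each tested at 97.2%.

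| Assumed rates | As coded | Correct |
|---|---|---|
| all four arms 5% | 1.4% | 1.2% |
| all four arms 10% | 3.3% | 2.9% |
| all four arms 20% | 4.1% | 3.2% |
| products 5%, saline 1% | 2.8% | 2.2% |
| products 10%, saline 1% | 10.5% | 6.3% |
| products 20%, saline 3% | 21.3% | 6.8% |

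**The case against.** The strongest reply is that this is a slip in an illustration with invented counts. The governing sentence names the right quantity, and a competent programmer would follow it. Several things must also happen before the error can matter: the overall Fisher test must be significant, the optional pairwise step must be taken, the score method must be preferred to pairwise Fisher tests (which the SAP equally allows and which would not carry this error), and the argument pattern must be copied. The result is informational and feeds no efficacy criterion or safety decision. If more than half the sites in an arm reacted, the coded proportion would exceed 1 and the mistake would show itself.

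The high-rate scenarios can also be questioned. The SAP says the interval may be calculated by category and time point, where rates cannot exceed the any-category rate and may be well below it. The per-pair error rates leave out the Fisher gate, the count of 28 pairs weights likely and unlikely results alike, and the largest gated gap needs products at 20% and saline at 3%.

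All of this stands as a limit on importance. None of it makes the call right: the SAP's printed interval is wrong for the SAP's own table, and the code contradicts the quantity named in the same section.

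**Conclusion.** The concern holds, as a minor error. The call passes non-positive counts where sample sizes belong, and the printed interval carries the mistake. In the example the effect is small and no conclusion changes. In reuse the error in declared differences runs one way, towards differences that are not there. It is slight near a 5% reaction rate and becomes large only at higher rates, chiefly when saline reacts less than the three products.

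The recomputed intervals rest only on the SAP's figures. The error rates rest on assumptions: the true reaction rates, 36 sites per arm, independence between arms (each subject contributes two treatments, so actual rates may differ) and, for the gated figures, testing three product pairs at 97.2%. The overall Fisher test is coded correctly, and the efficacy analyses are unaffected.

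**What to change.** In SAP 7.3.4, change the call to `diffscoreci(2, 36, 1, 36, conf.level = 0.972)` and replace the printed limits with -0.1160526 and 0.1806500. Add a sentence saying that the second and fourth arguments are the total sites analysed in each arm, that is, the row sums of the example table. Any program already drafted from the example should be checked for the same substitution.

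The cost is two arguments, one line of output and a sentence; data, design and conduct are untouched.

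Two clarifications could be made at the same time, though the correction does not depend on them. The SAP could say which adjustment and which set of comparisons give 97.2%. The scope of the irritation comparison could also be aligned: Protocol 7.5 covers four treatments ("Differences between both Investigational Products, Active Control, and Negative Control will be evaluated on skin irritation data"), as SAP 7.3.4 does, whereas Protocol 15.4 makes follow-up depend on whether Fisher's "exact test shows statistically significant skin irritation between the three study products".
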